## 4.0 PARTICIPANT ENROLLMENT

---

**NOTE: Sites must meet activation requirements prior to enrolling participants.**

### 4.1 Pre-Enrollment Informed Consent and Screening Procedures

Diagnostic or laboratory studies performed exclusively to determine eligibility will be done only after obtaining written informed consent. Studies or procedures that are performed for clinical indications (not exclusively to determine study eligibility) may be used for baseline values and/or to determine pre-eligibility, even if the studies were done before informed consent was obtained.

The informed consent process is to be fully documented (see [Section 17.4](#)), and the prospective participant must receive a copy of the signed informed consent document. Screening procedures are listed in [Section 10.0](#) (Study Calendar).

### 4.2 Participant Enrollment

#### 4.2.1 COH DCC Availability and Contact Information

Eligible participants will be registered on the study centrally by the Data Coordinating Center (DCC) at City of Hope. DCC staff are available **between the hours of 8.00 am and 5.00 pm PST, Monday through Friday (except holidays).**

- E-mail: [[contact]](mailto:[contact])

#### 4.2.2 Slot verification and reservation

A designated study team member should email the DCC to verify current slot availability, and to reserve a slot for a specific prospective subject (provide DCC with subject initials), including a tentative treatment date. Slots can only be held for a limited time, at the discretion of the study PI.

The DCC should be notified of cancellations of prospective participants holding slots as soon as possible.

#### 4.2.3 Registration Process

Allow up to 24 hours for the DCC to review eligibility. To register a participant the subsequent procedure is to be followed:

1. The study team should contact the DCC via email to provide notification regarding the pending registration and communicate desired timeline of the registration, especially if it must be completed promptly to meet the registration window.
2. The study team will email a **Complete Registration Packet** to the DCC, which consists of a copy of the following documents:
  - Registration Cover Sheet ([Appendix E](#))
  - Completed eligibility checklist (printed from [Section 3.0](#) of the protocol) with required signature(s)
  - Signed Informed Consent
  - Signed HIPAA authorization form (if separate from informed consent)
  - Signed subject's bill of Rights (California only)
3. When all source documents are received, the DCC will review and work with the study team to resolve any missing elements. Any missing documents may delay review and registration. A participant failing to meet all requirements will not be registered and the study team will be immediately notified.
4. The DCC will send a Confirmation of Registration Form, including the Subject Study Number to:
  - The study team: Site Lead Investigator, treating physician/ sub-investigator, protocol nurse, CRC and pharmacy (as needed).

- The COH Study PI and COH study team designees (including but not limited to study monitor(s) and statistician(s)).

5. Upon receipt of the Confirmation of Registration Form, COH study team will register the patient in OnCore. The DCC will register non-COH patients in OnCore.

#### 4.3 Screen Failures and Registered Participants Who Do Not begin Study Treatment

Notify the DCC immediately if the participant screen fails after registration or if the participant does not start treatment.

For non-COH sites, the reason for screen failure will be documented in the registration coversheet ([Appendix E](#)) and submitted to the DCC.

Issues that would cause treatment delays should be discussed with the Study Principal Investigator.

### 5.0 TREATMENT PROGRAM

---

#### 5.1 Treatment Program Overview

This is a multicenter, open-label, single-arm Phase 2 trial with acalabrutinib for patients with CLL with relapsed or refractory AIHA. Treatment will be administered on an out-patient basis (in-patient administration is allowed if deemed necessary by the Investigator). Participants will be followed at least every 4 months after removal from study drug until 12 months after end of treatment, introduction of next treatment (including standard-of-care BTK inhibitors) for AIHA or CLL, or death, whichever occurs first.

#### 5.2 Cycle Definition

The treatment cycle will be 28 days. Cycle 1 Day 1 is defined as the first day of acalabrutinib administration, and should occur within 30 days of consent. The cycle day count will continue despite a hold in acalabrutinib administration due to toxicities (See [Section 7.2](#)). However, the next cycle will be delayed as long as acalabrutinib is held and will start once acalabrutinib is restarted.

#### 5.3 Treatment Plan

Eligible participants enrolled in this study will receive acalabrutinib (100 mg PO BID) on an *out-patient* basis (however, treatment may also be given inpatient). On-study treatment with acalabrutinib will continue for up to 12 28-day cycles. Participants will be considered off-treatment once study drug is permanently stopped. Treatment with acalabrutinib may be continued beyond 12 cycles, for a maximum of 36 cycles, if the study participant might benefit from ongoing therapy in the opinion of treating physician (e.g., ongoing therapy for CLL with R/R AIHA is required). Participants will be followed for an additional 12 months from time of last administration of study drug.

Regimen Description				
Agent	Dose	Route*	Schedule	Cycle Length
Acalabrutinib	100 mg	PO, every 12 hours	Continuous	28 days

#### 5.4 Agent Administration

Acalabrutinib capsules should be taken orally twice daily with 8 ounces (approximately 240 mL) of water. The capsules should be swallowed whole and participants should not attempt to open capsules or dissolve them in water. If a dose is missed by more than 3 hours, participants should wait and take next dose at regularly scheduled time. Do not make up for missed dose.

Participants will self-administer oral study agent, acalabrutinib, and are required to maintain a medication diary to assess compliance (refer to [Appendix D](#)). Participants will receive instruction on how to administer study drug

from a physician, clinical research nurse, or other designated, qualified healthcare provider. Participants will be provided with a medical diary and are required to record the date, dose, and the time of the ingestion.

## 5.5 Assessments and Special Monitoring

For a detailed list of all study procedures including timing and windows, see [Section 10.0](#).

**Note:** Initiate a new cycle after all procedures/safety assessments have been completed.

## 5.6 Duration of Therapy and Criteria for Removal from Protocol Therapy

Participants will receive protocol therapy until one of the below criteria are met:

- Completed protocol therapy (see [Section 5.3](#))
- AIHA relapse or progressive disease for CLL
- Participant is deemed intolerant to protocol therapy because of toxicity, despite dose modification/delay
- General or specific changes in the patient's condition which render the patient unacceptable for further treatment in the judgment of the investigator
- Withdrawal of consent for further protocol therapy (See [Section 17.5](#))

Once participants meet criteria for removal from protocol therapy, the participant should then proceed to End of Treatment assessments, and then to follow-up (Refer to the Follow-Up section below).

Documentation of the reason for discontinuing protocol therapy and the date effective should be made in the Electronic Health Record/medical record and appropriate eCRF.

The COH DCC and the Study PI should be promptly notified of the change in participant status.

## 5.7 Follow-Up

All participants will enter follow-up after completing End of Treatment assessments (per Study Calendar in [Section 10.0](#) footnote d), until one of criteria in Section 5.8 below is met.

Assessment time points and windows are detailed in [Section 10.0](#).

## 5.8 Duration of Study Participation

Study participation may conclude when any of the following occur:

- Completion of study activities (treatment and 12 months of follow-up after protocol treatment)
- Withdrawal of consent (See [Section 17.5](#))
- Start of new therapy for either AIHA or CLL (including standard-of-care BTK inhibitors)
- Participant is lost to follow-up. All attempts to contact the participant must be documented.
- At the discretion of the investigator for safety, behavioral, study termination or administrative reasons

Documentation of the reason for discontinuing study participation and the date effective should be made in the Electronic Health Record/medical record and appropriate eCRF.

The COH DCC and the Study PI should be promptly notified of the change in participant status.

## 5.9 Prohibited and Concomitant Therapies/Medications

### 5.9.1 Allowed concomitant medications

Medications required to treat AEs, manage cancer symptoms, concurrent diseases and supportive care agents, such as pain medications, anti-emetics and anti-diarrheals are allowed in general. The participant must be told to

notify the investigational site about any new medications begun after the start of the study treatment. Each participant's medication and supplement profile should be reviewed by investigator and/or an oncology trained pharmacist to ensure compliance with this aspect of care. If concomitant therapy must be added or changed, including over-the-counter medications or alternative therapies, the reason and name of the agent/therapy should be recorded in the eCRF and documented in the Electronic Health Record/medical record.

### 5.9.2 Prohibited medications, treatments and procedures

Patients will not receive any other therapy for CLL besides the study therapy.

Participants are prohibited from receiving the following therapies during screening and for the duration of their participation in this study:

- Any anti-cancer systemic chemotherapy (e.g., bendamustine, cyclophosphamide, pentostatin, or fludarabine), or targeted agents (venetoclax, duvelisib, etc.)
- Any immunotherapy (e.g., rituximab, GA101, alemtuzumab, or ofatumumab)
- Bone marrow transplant or CAR T-cells
- Any other experimental therapy, or radiation therapy while receiving acalabrutinib
- Vitamin K antagonists (e.g., warfarin)

### 5.9.3 Cautionary medications, treatments and procedures

Co-administration of acalabrutinib with a proton pump inhibitor should be avoided. Co-administration of acalabrutinib with a strong or moderate CYP3A inhibitors may increase acalabrutinib plasma concentrations resulting in increased toxicity. Use of strong or moderate CYP3A inhibitors should be avoided. Conversely, co-administration of acalabrutinib with a strong CYP3A inducer should be avoided as this may decrease acalabrutinib concentrations. Refer to **Table 5.9.1** for examples of proton pump inhibitors, and CYP3A inhibitor and inducers.

**Table 5.9.1. Examples of proton pump inhibitors, and CYP3A inhibitors and inducers**

Proton-pump inhibitors
Omeprazole, Lansoprazole, Pantoprazole, Rabeprazole, Esomeprazole, Dexlansoprazole
Strong CYP3A Inhibitors
Ketoconazole, Clarithromycin, Itraconazole, Nefazodone, Saquinavir, Ritonavir, Indinavir, Nelfinavir, Voriconazole, Lopinavir, Telithromycin, Conivaptan, Posaconazole, Boceprevir, Telaprevir, Cobicistat, Idefalisib, Grapefruit, Starfruit, Seville Oranges
Moderate CYP3A Inhibitors
Erythromycin, Verapamil, Diltiazem, Cyclosporine, Ciprofloxacin, Fluvoxamine, Fluconazole, Aprepitant, Imatinib, Nilotinib, Dronedarone, Crizotinib, Atazanavir, Letermovir, Duvelisib
Strong CYP3A Inducers
Phenytoin, Carbamazepine, Rifampin, Mitotane, Fosphenytoin, St John's Wort, Enzalutamide, Lumacaftor
 This is not an exhaustive list. Investigators should consult additional resources (e.g., website, drug label) for a full list or for more info on individual drugs.
 Refer to Flockhart Table™ for a more detailed list of CYP3A inducers and inhibitors ( https://drug-interactions.medicine.iu.edu/Main-Table.aspx ).

### 5.10 Supportive care

With the exception of prohibited therapies (refer to Prohibited therapies sub-section above), participants should receive prophylactic or supportive as clinically indicated per institutional policies.

### **5.10.1 Corticosteroids**

Participants are not permitted to be receiving chronic corticosteroids (>2 weeks within the 4 week period prior to first dose of study medication; at dosages equivalent to prednisone >60 mg/day) at time of screening and enrollment on to this study – see [Section 3.2](#). Concomitant use of corticosteroids for management of AIHA in conjunction with study drug is permitted at this dose, but it is anticipated that a taper will occur while patient is receiving acalabrutinib, and should be completed by the end of 8 weeks on study to a dose of ≤20 mg/day of prednisone or equivalent. The use of corticosteroids for treating AIHA should be in accordance with institutional standards.

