
Autoimmune hemolytic anemia (AIHA) is a life-threatening disease with an incidence of 1-3 per 100,000 persons per year. In addition to idiopathic AIHA, a number of underlying conditions have been associated with this disorder, including viral infections, autoimmune and connective tissues diseases, and lymphoproliferative disorders. AIHA is particularly common among patients with chronic lymphocytic leukemia (CLL) with an incidence of ~2.3% as reported in a recent retrospective analysis of 1750 patients. First-line therapy of AIHA typically consists of corticosteroids, which induce initial responses in 70%-85% of patients with warm AIHA; however, only one-third of patients remain in long-term remission after stopping corticosteroids, and a further 50% require maintenance doses. Subsequent lines of immunosuppressive therapy carry initial response rates from 40-60%, though relapses are similarly common. Therefore, in the relapsed/refractory setting, safe and effective treatments for AIHA are needed. Ibrutinib, a small molecule inhibitor of Bruton tyrosine kinase (BTK), inhibits B-cell activity and has been shown to inhibit production of auto-antibodies in murine models of autoimmunity, suggesting their potential efficacy in multiple autoimmune conditions. Preliminary evidence suggests that ibrutinib may be efficacious in treatment of CLL-associated AIHA, as 50% of patients who presented with hemolysis and received therapy with the BTK inhibitor were able to discontinue immunosuppressive therapy. A second-generation selective BTK inhibitor, acalabrutinib, may be associated with fewer off-target effects including diminished frequency of side effects including bleeding and atrial fibrillation, and showed increased efficacy against AIHA in a murine model. This study will assess if acalabrutinib can increase hemoglobin and reduce transfusion requirements in patients with relapsed or refractory AIHA.
	
Treatment Description	

Eligible participants enrolled in this study will receive acalabrutinib (100 mg, PO BID) for 12 cycles. Participants that experience disease progression or unacceptable toxicities will discontinue study drug and be removed from study. Treatment with acalabrutinib may be continued beyond 12 cycles, for a maximum of 36 cycles, if the study participant might benefit from ongoing therapy in the opinion of treating physician (e.g., ongoing therapy for CLL is required).
	
Objectives	

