### 3.2 Exclusion Criteria

#### Prior and concomitant therapies

- \_\_\_ 1. therapeutic anticancer antibodies within 2 weeks;
- \_\_\_ 2. radio- or toxin-immunoconjugates within 10 weeks;
- \_\_\_ 3. BH3-mimetic venetoclax, PI3K inhibitors and other “targeted” therapy– within 6 half-lives;
- \_\_\_ 4. Ibrutinib, acalabrutinib or another BTK inhibitor within 12 months
- \_\_\_ 5. Patients on stable chronic AIHA treatments are allowed provided the dose has not changed in the 4 weeks prior to enrollment
- \_\_\_ 6. Allogeneic stem cell transplant within 1 year prior to Day 1 of protocol therapy, or ongoing immunosuppressive therapy for cGVHD
- \_\_\_ 7. Chemotherapy, radiation therapy, biological therapy, immunotherapy within 21 days prior to Day 1 of protocol therapy

\_\_8. Strong CYP3A4 inducers/ inhibitors. If the patient requires a strong CYP3A inhibitor/inducer, they should not be enrolled even if it could be held for 14 days before the first dose of study drug.

\_\_9. Proton pump inhibitors (but patients who switch to H2-receptor antagonists or antacids are eligible for enrollment).

\_\_10. Chronic use of corticosteroids (>2 weeks) in excess of prednisone 60 mg/day or its equivalent within 4 weeks prior to start of study therapy. Rescue steroids are allowed during trial.

\_\_11. Vitamin K antagonists

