
a. Ideally the clinic visit and all the study requirements should be performed on Day 1 of each cycle as indicated, but may be performed within 7 days before or after the scheduled day. Each treatment cycle is 28 days
 
b. Screening activities to occur within 30 days prior to the start of protocol therapy.
 
c. Protocol therapy may last up to 12 cycles, until unacceptable toxicity or disease progression (see Section 5.6 for more comprehensive list). At the end of 12 cycles, treatment with acalabrutinib may be continued if the study participant might benefit from the ongoing therapy in the opinion of the treating physician.
 
d. An End of Treatment (EOT) visit is required for safety assessments for any subjects who permanently discontinue study drug for any reason, including disease progression. This visit should occur at 30 (<math>\pm 7</math>) days from time of the last dose of study drug to monitor for resolution or progression of AEs and to document the occurrence of any new events, regardless of whether the subject receives a new CLL therapy or demonstrates disease progression within this timeframe. Subjects who withdraw consent for study treatment should still be encouraged to complete the EOT assessments, but these assessments cannot be mandated if subject consent for further study participation is withdrawn.
 
e. Follow-up assessments are to occur in accordance with standard of care, with participants visits occurring at least every 4 months, up to 12 months from time last dose of study drug.
 
f. Informed consent process to be fully documented (see Section 17.4). Informed consent must occur prior to any research only (non-SOC) screening procedures.
 
g. A medical history will be obtained by the investigator or qualified designee. To include information on demographics, all active conditions, and any condition diagnosed within the prior 10 years that are considered to be clinically significant by the Investigator. Details regarding the participant's cancer will be recorded separately and not listed as medical history.
 
h. Eligibility criteria are detailed in Section 3.0.
 
i. Registration into a COH clinical trial management system (CTMS)
 
j. Document the following disease-specific information: number of prior treatment regimens for CLL and AIHA; drugs previously used in the therapy of CLL and AIHA; including (if available): therapy dates, and response, concomitant autoimmune disorders, including hematologic (immune thrombocytopenia, immune-mediated neutropenia) and non-hematologic (e.g., rheumatoid arthritis and other rheumatologic conditions; inflammatory bowel disease [Crohn's disease, ulcerative colitis]), History of ibrutinib intolerance (present versus not), Rai stage at diagnosis (if known) and the time of study entry.
 
k. Current list of medications will be acquired concurrent with medical history. See Section 5.9 for concomitant medication restrictions and guidelines. Baseline transfusion requirements must be assessed prior to start of study drug. Transfusion requirements prior to study start up to 6 months will be collected/documents, if available. Transfusion requirement will be assessed on day 1 of each cycle and number of units of PRBCs and platelets transfused during the previous cycle will be documented. Enter new medications started during the trial through the end of treatment visit. Record all medications taken for grade 3 and 4 SAEs.
 
l. Physical examination must be performed by a medically qualified individual such as a licensed physician, Physician's Assistant or advanced Registered Nurse Practitioner as local law permits. Baseline complete physical exam per institutional standards and may include evaluating: weight, general appearance, head, ears, eyes, nose, throat, neck, skin, cardiovascular system, respiratory system, gastrointestinal system, and nervous system. Height is only required as part of screening. Weight should be recorded at each visit. More extensive physical exams will be performed if guided by the development of new symptoms.
 
m. Vital signs: blood pressure, heart rate, temperature, and oxygen saturation by pulse oximetry.
														

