**APPENDIX B: AIHA RESPONSE CRITERIA**

Treatment response will be determined per the investigators' assessment, according to Barcellini et al.

AIHA Complete Response (CRAIHA):	Hemoglobin >12 g/dL, AND no transfusion requirements. No laboratory evidence of ongoing hemolysis (haptoglobin, indirect bilirubin WNL, reticulocyte count <1.5 ULN)
AIHA Partial Response (PRAIHA):	Hemoglobin level ≥10 g/dL (without transfusions), OR hemoglobin increase of at least 2 g/dL above pretreatment level, Presence of laboratory evidence of ongoing hemolysis.

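### Steroid dose enters neither the AIHA response criteria nor any analysis, so a 6-cycle response on continuing prednisone scores the same as one off steroid

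*Combined protocol and SAP*

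**What the plan says.** **Steroid use.** Section 5.10.1 permits corticosteroid for AIHA together with study drug. It anticipates a taper that "should be completed by the end of 8 weeks on study to a dose of ≤20 mg/day of prednisone or equivalent". It sets no taper to zero, no stop date and no steroid-free period before a response assessment, and it adds: "The use of corticosteroids for treating AIHA should be in accordance with institutional standards". In Section 3.2, exclusion 10 notes: "Rescue steroids are allowed during trial". Exclusion 5 reads: "Patients on stable chronic AIHA treatments are allowed provided the dose has not changed in the 4 weeks prior to enrollment". Inclusion 4 in Section 3.1 admits patients with hemoglobin above 10 g/dL who depend on transfusion or maintenance therapy to stay there.

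**Response.** Appendix B defines complete and partial response by hemoglobin, transfusion and hemolysis markers. Partial response needs untransfused hemoglobin of at least 10 g/dL or a "hemoglobin increase of at least 2 g/dL above pretreatment level". Sections 11.1 and 11.2 take the response rates after 3, 6 and 12 cycles from these criteria. Sections 12.4.1 and 12.4.2 contain no steroid-dose, steroid-free or steroid-sparing analysis.

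**Data capture.** The Section 10.0 calendar has a concurrent medication review at screening and treatment visits. Footnote k takes a baseline medication list and then says: "Enter new medications started during the trial through the end of treatment visit". When therapy is added or changed, Section 5.9.1 says "the reason and name of the agent/therapy should be recorded in the eCRF". Table 13.3 lists a concomitant medication form. None of these names dose as a required item.

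**The concern.** The primary result is one response rate compared with a fixed 30%, with no control arm to absorb the effect of background treatment. Any patient whose hemoglobin is held up by prednisone after 6 cycles adds directly to that rate.

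The protocol handles the other main form of support differently. Appendix B requires the 10 g/dL limb to be met without transfusion, footnote k records units transfused each cycle, and Section 12.4.2 compares transfusion frequency before and during treatment. Steroid gets none of these.

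The omission also leaves a gap against the trial's own rationale. Section 2.1.3 supports BTK inhibition with two retrospective ibrutinib cohorts in which 19 of 22 and 8 of 12 patients were able to stop therapy for autoimmune cytopenia. No endpoint in this trial measures stopping or reducing such therapy.

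**Working it through.** **1. The plan's own figures.** Section 12.2 gives n = 20, a cutoff of 10 responders, a null rate of 0.30, an alternative of 0.60 and one-sided alpha of 0.05. The formula is P(X ≥ 10) = Σ C(20,k) p^k (1−p)^(20−k), summed over k = 10 to 20.

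- p = 0.30 gives 0.0480 (stated 0.048).
- p = 0.60 gives 0.8725 (stated about 87%).
- A cutoff of 9 gives 0.1133 at p = 0.30, so 10 is the smallest valid cutoff.

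The design arithmetic is right. The question is what a response means.

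**2. Two patients under Appendix B.** Both have untransfused hemoglobin of at least 10 g/dL, with hemolysis markers still present, after 6 cycles. One takes 20 mg/day of prednisone, which Section 5.10.1 allows; the other takes none. Both meet partial response, and nothing in Sections 11 or 12 separates them.

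**3. Timing.** The taper is expected to end at 8 weeks. Three cycles are 3 × 28 = 84 days, or 12 weeks, so the 3-cycle rate is read 4 weeks after that. Six cycles are 24 weeks, 16 weeks after it. Permitted steroid at up to 20 mg/day can run through both assessments.

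**4. Size, under assumptions.** The documents give no rate of steroid-supported response. Both versions below start from a true rate of 0.30 without steroid support.

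(a) Steroid adds a fixed number of percentage points, so p = 0.30 + a.

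| a | p | P(≥10 of 20) |
|---|---|---|
| 0.05 | 0.35 | 0.122 |
| 0.10 | 0.40 | 0.245 |
| 0.15 | 0.45 | 0.409 |
| 0.20 | 0.50 | 0.588 |

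In expected patients, this runs from 0.05 × 20 = 1 to 0.20 × 20 = 4 extra responders.

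(b) A share s of the patients who would otherwise not respond is counted as responding, so p = 0.30 + 0.70s.

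| s | p | P(≥10 of 20) |
|---|---|---|
| 0.05 | 0.335 | 0.095 |
| 0.10 | 0.37 | 0.165 |
| 0.15 | 0.405 | 0.260 |
| 0.20 | 0.44 | 0.374 |

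The versions differ because a 20% share of non-responders adds 0.70 × 0.20 = 14 points, not 20.

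**5. Why not tighten the primary endpoint.** Suppose response on steroid counted as failure and a share d of responders were steroid-dependent, so p = 0.60(1 − d). Power at the current rule would be 0.721 at d = 10% (p = 0.54), 0.517 at 20% (p = 0.48) and 0.306 at 30% (p = 0.42). With 20 evaluable patients, a supportive analysis is the better place for the question.

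**The case against.** Several stronger readings are tempting, and the documents do not support them.

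- **That steroid use goes unrecorded, or could never be separated out later.** Medications are reviewed, listed at baseline and entered when new, added or changed, and a taper is a change. Exclusions 5 and 10 cannot be checked without the entry dose, and the data coordinating center reviews the eligibility checklist. The eCRF is not part of the documents and may hold dose, as may source records. What stands is narrower: the protocol does not require dose over time.
- **That about half of responders would be steroid-supported**, because the synopsis says "only one-third of patients remain in long-term remission after stopping corticosteroids, and a further 50% require maintenance doses". That figure describes first-line corticosteroid therapy, not relapsed or refractory AIHA in CLL. Section 2.1.2 also calls steroids relatively ineffective in cold AIHA, which is eligible here.
- **That every response on prednisone is doubtful.** On the main entry limb, patients have relapsed after or not responded to prednisone, have hemoglobin of 10 g/dL or less and show hemolysis. If such a patient enters on a stable dose and hemoglobin rises as the dose falls, prednisone is a poor explanation. The concern is greatest for patients entering above 10 g/dL on maintenance therapy, and for those whose steroid was recently started or is given as rescue. The maintenance examples named in inclusion 4 are not steroids, but the list is open-ended.
- **That the test is biased by a known amount.** The inputs to step 4 are assumed. Section 12.2 cites durable response in 20% to 30% of treated patients without stating steroid co-use, so the 30% benchmark may itself include steroid-supported responses. The net bias is unknown.

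It is also fair that the trial adopts published response criteria and leaves response to the investigator. But nothing tells investigators to weigh steroid dose when they score it.

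**Conclusion.** The gap is real and limited. Steroid at up to 20 mg/day may continue without an end date, rescue steroid is allowed with no stated consequence for response, and no response criterion, endpoint or analysis uses steroid dose. A 6-cycle response on steroid therefore counts the same as one off steroid, and the specified data do not guarantee that the two can be told apart.

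The effect on the decision cannot be estimated from the documents. The ranges of 0.12 to 0.59 and 0.095 to 0.37, against a nominal 0.048, rest wholly on assumed inputs. They show only that a few such patients among 20 could change the conclusion. The sample size, the cutoff and the validity of the exact test for the endpoint as defined are unaffected. This is a worthwhile addition to data capture and reporting, not grounds to discard the primary analysis.

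**What to change.** - **Section 10.0, footnote k:** require the daily prednisone-equivalent dose, with dates of change and including rescue, at screening, C1D1 and Day 1 of each cycle.
- **Section 12.4.1:** keep the primary test and decision rule. Pre-specify, as supportive, the AIHA response rate off corticosteroids at the 6-cycle assessment with an exact 95% confidence interval. Cross-tabulate primary responders by dose at C7D1 (0, above 0 to 20, above 20 mg/day). The 20 mg cut is the one already in Section 5.10.1 and is used here only for reporting.
- **Section 12.4.2:** summarise change from baseline in prednisone-equivalent dose at C4D1, C7D1 and C13D1.

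The cost is one eCRF field at existing visits, one supportive rate and two descriptive tables. The sponsor must accept that the off-steroid rate may be lower than the headline rate. No visit is added, and no change to steroid management is proposed.
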